8.4 Study drug exposure

The study drug exposure will be presented using the variables listed below:

Variable	Formula
Total dose planned per protocol for patients enrolled under protocol amendment 1 (mL) [PLANNED_DOSE]	
Weight (in kg) * 3.68 mL/kg for patients who agreed to do the extension
 
Where 3.68 mL/kg=
 $(2 \text{ days} * 2.5 \text{ mg/kg bid} * 2 + 4 \text{ days} * 5 \text{ mg/kg bid} * 2 + 7 \text{ days} * 7.5 \text{ mg/kg bid} * 2 + 167 \text{ days} * 10 \text{ mg/kg bid} * 2) / 950 \text{ mg/mL}$ 
Or
 
Weight (in kg) * 1.07 mL/kg for patients who stopped the study at 8 weeks
 
Where 1.07 mL/kg=
 $(2 \text{ days} * 2.5 \text{ mg/kg bid} * 2 + 4 \text{ days} * 5 \text{ mg/kg bid} * 2 + 7 \text{ days} * 7.5 \text{ mg/kg bid} * 2 + 43 \text{ days} * 10 \text{ mg/kg bid} * 2) / 950 \text{ mg/mL}$
Total dose planned for patients enrolled under protocol amendment 1 (mL) based on visits actually performed	$\text{weight (in kg)} * \sum_{i=1}^{10} \text{planned dose (mg/kg bid) documented at visit i} * 2 * (\text{visit date (i + 1)} - \text{visit date (i)})$
Total dose planned for patients enrolled under protocol amendment 2 (mL) [PLANNED_DOSE]	
Weight (in kg) * 3.73 mL/kg for patients who agreed to do the extension
 
Where 3.73 mL/kg=
 $(2 \text{ days} * 5 \text{ mg/kg bid} * 2 + 7 \text{ days} * 7.5 \text{ mg/kg bid} * 2 + 171 \text{ days} * 10 \text{ mg/kg bid} * 2) / 950 \text{ mg/mL}$ 
Or

Variable	Formula
	
Weight (in kg) * 1.11 mL/kg for patients who stopped the study at 8 weeks
 
Where 1.11 mL/kg=
 $ \begin{aligned} & (2 \text{ days} * 5 \text{ mg/kg bid} * 2 \\ & + 7 \text{ days} * 7.5 \text{ mg/kg bid} * 2 \\ & + 47 \text{ days} * 10 \text{ mg/kg bid} * 2) / 950 \text{ mg/mL} \end{aligned} $
Total dose planned for patients enrolled under protocol amendment 2 (mL) based on visits actually performed	$ \text{weight (in kg)} * \sum_{i=1}^8 \text{planned dose (mg/kg bid) documented at visit } i * 2 * (\text{visit date } (i+1) - \text{visit date } (i)) $
Total dose taken (mL) [DOSE_TAKEN]	$ \sum_{j=1}^{\# \text{ bottles returned}} \frac{78 \text{ g} - \text{bottle weight in g (j)}}{0.95 \text{ [g/mL]}} $ 
If there is no bottle weight and the reason is:
 
 • 'Bottle broken', imputed weight to 48g • 'Unused bottle', imputed weight to 78g 
Note: 'Already weighted' should not be considered.
 $ + \sum_{k=1}^{\# \text{ bottles unreturned}} \frac{78 \text{ g} - \text{imputed bottle weight (k)}}{0.95 \text{ [g/mL]}} $ 
Imputed weight if the status of the unreturned IMP bottle is:
 
 • 'Unused', imputed weight to 78g • 'Empty', imputed weight to 48g • Other reasons, i.e., 'Used per instructions', 'Not used per instructions', 'Unknown' must be reviewed during DRM.
Compliance global (%)	[DOSE_TAKEN] / [PLANNED_DOSE]
# days during which patients were taking the IMP	Last date under medication – first date under medication – the sum of all temporary interruption (end date of interruption – start date of interruption +1)
# patients who did not complete 8 weeks on IMP	# of patients with Premature withdrawal of study treatment form completed before the Week 8 visit date
# patients who stopped the IMP prematurely (i.e. prior to or at week 8)	# of patients with Premature withdrawal of study treatment form with a premature withdrawal date \leq Week 8 visit date

Variable	Formula
# patients with highest tolerated IMP dose up to Week 8	
# of patients for whom the maximum dose taken up to the week 8 visit date was:
 
 • 10mg/kg of body weight b.i.d. • 7.5mg/kg of body weight b.i.d. • 5.0mg/kg of body weight b.i.d.
# patients with highest tolerated IMP dose over the complete follow-up period	
# of patients for whom the maximum dose taken up to the last IMP intake was:
 
 • 10mg/kg of body weight b.i.d. • 7.5mg/kg of body weight b.i.d. • 5.0mg/kg of body weight b.i.d.

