## **6.4 Study Medication**

CardiolRx™ (cannabidiol) solution contains cannabidiol at a concentration of 100 mg/mL. Inactive ingredients include medium-chain triglyceride (MCT) oil and Vitamin E.

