## 7 STUDY PLAN

## 8 INVESTIGATIONAL PRODUCTS, DOSE AND DURATION OF TREATMENT

### 8.1 *Investigational Product*

CardiolRx™ is synthetically produced. It contains cannabidiol oil in a concentration of 100 mg/mL and is free of THC (<5 ppm).

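### SAP 8.4 converts planned mg to mL with the solution's density (950 mg/mL) instead of its drug concentration (100 mg/mL), so full compliance prints as about 950%

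*SAP*

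**What the plan says.** SAP Section 8.4 defines planned dose in mL as body weight times a fixed factor. There are four factors: 3.68 and 1.07 mL/kg for Amendment 1 (26 and 8 weeks), and 3.73 and 1.11 mL/kg for Amendment 2. Two of them read "Weight (in kg) * 3.73 mL/kg for patients who agreed to do the extension" and "Weight (in kg) * 1.11 mL/kg for patients who stopped the study at 8 weeks". Each is written out as days × mg/kg × 2, summed over the titration steps and divided by 950 mg/mL.

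The protocol gives the strength twice. Section 6.4 says the "solution contains cannabidiol at a concentration of 100 mg/mL", and Section 8.1 says "It contains cannabidiol oil in a concentration of 100 mg/mL".

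Dose taken, also in mL, is the weight lost from each bottle (78 g minus the returned weight) divided by 0.95 g/mL. Global compliance is the plain ratio "DOSE_TAKEN] / [PLANNED_DOSE", with no rescaling.

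The same table has two planned totals based on visits performed, both labelled mL. It also has an imputation rule that opens "If there is no bottle weight and the reason is", under which a broken bottle is given 48 g, the same weight as an empty one.

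**The concern.** To turn mg of drug into mL of solution, one divides by the mg of drug in each mL. The SAP divides by 950 mg/mL, which is 0.95 g/mL in other units: the mass of a mL of solution, not its cannabidiol content. The density belongs in the numerator, where grams of solution become mL. In the denominator it shrinks the planned volume about 9.5-fold.

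The results feed SAP Table 15 (study drug exposure). In an open-label, single-arm pilot meant to assess tolerance and to inform a randomized trial, readers need to know how much drug patients took. As specified, the planned-volume and compliance entries are wrong for every patient, and a printed value near 100% would mean very low intake.

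**Working it through.** **Inputs.** Day counts and dose steps: SAP 8.4. Concentration, 100 mg/mL: Protocol 6.4 and 8.1. Bottle-weight conversion, 0.95 g/mL, and bottle weights of 78 g (unused) and 48 g (empty): SAP 8.4. Bottle size, 30 mL: Protocol 8.4.1.

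**Step 1: reproduce the SAP's factors.** Scheduled mg/kg = sum of days × mg/kg × 2.

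- Amendment 1, 26 weeks: 2×2.5×2 + 4×5×2 + 7×7.5×2 + 167×10×2 = 3495
- Amendment 1, 8 weeks: 10 + 40 + 105 + 43×10×2 = 1015
- Amendment 2, 26 weeks: 2×5×2 + 7×7.5×2 + 171×10×2 = 3545
- Amendment 2, 8 weeks: 20 + 105 + 47×10×2 = 1065

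**Step 2: compare the divisors.** The last column is the ÷100 figure over the printed factor, that is, what compliance shows when every scheduled dose is taken. Weight cancels.

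| Group | mg/kg | ÷950 | SAP prints | ÷100 (mL/kg) | Printed compliance |
|---|---|---|---|---|---|
| Amendment 1, 26 wk | 3495 | 3.679 | 3.68 | 34.95 | 949.7% |
| Amendment 1, 8 wk | 1015 | 1.068 | 1.07 | 10.15 | 948.6% |
| Amendment 2, 26 wk | 3545 | 3.732 | 3.73 | 35.45 | 950.4% |
| Amendment 2, 8 wk | 1065 | 1.121 | 1.11 | 10.65 | 959.5% |

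Three factors reproduce exactly with 950, so 950 was used in the calculation and is not a misprint for 100. The fourth should round to 1.12 on the SAP's own formula.

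**Step 3: scale (Amendment 2, 26 weeks, assumed 70 kg).** The SAP plans 3.73 × 70 = 261.1 mL, about 9 bottles of 30 mL. The dose and concentration require 35.45 × 70 = 2481.5 mL, about 83 bottles. True 30% adherence prints as 0.30 × 35.45 / 3.73 = 285%, and true 10% as 95%. A printed 100% means 3.73 / 35.45 = 10.5% of the planned drug was taken.

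**Step 4: visit-based totals.** These are weight × the sum of (mg/kg × 2 × days between visits), with no division by a concentration. The result is in mg. Read as mL, it is 100 times too large.

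**Step 5: bottle rules.** A bottle imputed at 48 g counts as (78 − 48) / 0.95 = 31.6 mL taken. A 30 mL fill at 0.95 g/mL weighs 28.5 g, not 30 g. A broken bottle without a weight gets the same 31.6 mL, so all of its contents count as swallowed.

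**The case against.** The one reading that would rescue 950 is that the protocol's mg/kg of CardiolRx means mg of solution. At an assumed 70 kg, 10 mg/kg twice daily would then be 1400 / 950 = 1.47 mL/day, or about 147 mg of cannabidiol. Protocol Section 3.5 calls 100 mg twice daily low against 600–800 mg/day in other human studies. Reading mg as cannabidiol gives 1400 mg/day. The rescue contradicts the trial's own rationale and fails.

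The objections to the impact are stronger, and parts of them stand:

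- The error is a nearly constant multiplier (9.49 to 9.59), so the ordering of patients is largely kept and true values can be recovered. A mean of 950% would be noticed, and SAP Section 9.1 requires senior statistical review of output. But correction would then be an unplanned change after the data are seen, and intake near 10% would still look normal.
- No visible analysis uses compliance. There is no per-protocol set, and the pain, CRP, adverse event and ECG outputs do not depend on it. Days on drug, premature stops and highest tolerated dose are also unaffected.
- The 949–959% range applies to the full titration. A patient correctly held at 5 mg/kg for 180 days takes 5 × 2 × 180 / 100 = 18.0 mL/kg, which prints as 483%. Even with the corrected factor, that patient prints as 51%.
- The 26-week factors use 180 days, not 182. At 182 days the Amendment 2 volume is 3585 / 100 = 35.85 mL/kg, a change of about 1%.
- The 31.6 versus 30 mL gap could reflect overfill, since no fill weight is given. The broken-bottle rule is a judgement, not an arithmetic error.

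**Conclusion.** The concern holds. All four planned-dose factors use the density where the drug concentration belongs. Planned volume is about 9.5 times too small, and compliance is inflated by the same amount for every patient: 949–959% for full intake of the full titration. This rests on the protocol's 100 mg/mL, on mg meaning mg of cannabidiol, and on accurate bottle weights. The SAP does not call 950 a density; that follows from its own 0.95 g/mL. The missing divisor in the visit-based totals is a second, separate unit error, which does not enter the compliance ratio.

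The damage is confined to the planned-dose and compliance rows of Table 15. Within those rows the formula cannot produce the quantity it names, so it must be corrected before the table is run. The 1.11 rounding, the broken-bottle rule and the 48 g weight are minor by comparison.

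**What to change.** In SAP Section 8.4:

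1. Divide by 100 mg/mL in all four planned-dose formulas and replace the factors with 34.95 and 10.15 mL/kg (Amendment 1) and 35.45 and 10.65 mL/kg (Amendment 2). Keep 0.95 g/mL for bottle weights only.
2. Divide both visit-based sums by 100 mg/mL so that they match their mL label.
3. Send broken bottles without a weight to the data review meeting, as unreturned bottles of unknown status already are, instead of imputing 48 g.
4. Reconcile the 48 g empty weight with a 30 mL fill, or state the overfill.
5. Note under Table 15 that the fixed factors assume the full titration over 180 days. Patients kept on a lower dose will show low values against them; the corrected visit-based total is the denominator that reflects the dose recorded at each visit.

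The cost is SAP wording and a few lines in the exposure program. No new patient data are needed; item 4 needs the bottle or fill specification.

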4.3 Study treatment assignment

Per protocol amendment 2, eligible patients would receive open label IMP (i.e. CardiolRxTM).

The dosing regimen was as follows:

- Day 1 p.m. to Day 3 a.m. dose: 5 mg/kg of body weight b.i.d. First dose to be taken in the evening of the screening visit (i.e. day 1)
- Day 3 p.m. dose to Day 10 a.m. dose: 7.5 mg/kg of body weight b.i.d. Dose titration if previous dose tolerated
- Day 10 p.m. dose to end of treatment period (a.m. dose at either week 8 or am dose week 26 if patient continued in the EP phase of the trial): 10 mg/kg of body weight b.i.d. Dose titration if previous dose tolerated

The morning and evening doses should be taken minimally 6 and maximally 18 hours apart. If the next higher dose after each study drug increase was not tolerated, the site could reduce the dose to the previous tolerated dose.

Difference between protocol amendments 1 and 2 and the (potential) impact on the statistical Analysis

Protocol amendment 1: Administration of IMP was planned as follows²:

- Day 1 p.m. dose to Day 3 a.m. dose: 2.5 mg/kg of body weight b.i.d.
- Day 3 p.m. dose to Day 7 a.m. dose: 5.0 mg/kg of body weight b.i.d.
- Day 7 p.m. dose to Day 14 a.m. dose: 7.5 mg/kg of body weight b.i.d.
- Day 14 p.m. dose to end of treatment period (a.m. dose at week 26, i.e Day 181): 10.0 mg/kg of body weight b.i.d

Impact on the statistical Analysis Plan:

The difference in the overall dose is an increase of 5% (i.e. starting dose was 2.5 mg/kg of body weight b.i.d for protocol amendment 1 and 5 mg/kg of body weight b.i.d for amendment 2). This may potentially impact on the primary endpoint at 8 weeks and on the total dose taken over the study duration.

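### SAP 8.4: the Amendment 2 Week 8 planned-dose constant is 1.12 mL/kg on its own inputs, not 1.11, and the 180-day extension count needs reconciling with 26 weeks

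*SAP*

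**What the plan says.** SAP section 8.4 (Study drug exposure) gives four constants for the total planned dose per kilogram, one for each combination of protocol amendment and planned duration. Each is printed with the days and doses behind it and a divisor of 950 mg/mL.

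- Amendment 2, Week 8: "1.11 mL/kg for patients who stopped the study at 8 weeks". The expansion below it opens "Where 1.11 mL/kg" and lists 2 days at 5, 7 days at 7.5 and 47 days at 10 mg/kg twice daily.
- Amendment 2, extension: "3.73 mL/kg for patients who agreed to do the extension", with 171 days at the top dose.
- Amendment 1, extension: "3.68 mL/kg for patients who agreed to do the extension", with 167 days at the top dose.
- Amendment 1, Week 8: 1.07 mL/kg, with 43 days at the top dose.

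The same section defines global compliance as the dose taken divided by the quantity labelled PLANNED_DOSE. That label is attached to these constants.

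On duration, SAP section 4.3 describes the end of the Amendment 1 regimen as "a.m. dose at week 26, i.e Day 181". The current protocol has treatment running to 26 weeks after the first dose (section 8.2), with an 18-week extension after the first 8 weeks (section 6.2).

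**The concern.** A constant printed next to its own inputs should follow from them. The Amendment 2 Week 8 constant does not. Because it sits in a denominator, a value that is too small pushes reported compliance up, and always in that direction.

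The day counts raise a second, separate question. The Week 8 schedules use exactly 8 × 7 days, but the extension schedules fall two days short of 26 × 7. If the shortfall is unintended, compliance for extension patients is also pushed up slightly.

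What is at stake is the accuracy of the exposure table. No efficacy estimate uses these figures.

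**Working it through.** **Inputs.** Days, doses and the divisor of 950 mg/mL are from SAP 8.4. Each dose is given twice daily, so the sum is days × mg/kg × 2.

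**Reproducing the four constants.**

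| Schedule | Days | Sum (mg/kg) | Sum/950 | Printed |
|---|---|---|---|---|
| Amendment 1, extension | 2+4+7+167 = 180 | 10+40+105+3340 = 3495 | 3.679 | 3.68 |
| Amendment 1, Week 8 | 2+4+7+43 = 56 | 10+40+105+860 = 1015 | 1.068 | 1.07 |
| Amendment 2, extension | 2+7+171 = 180 | 20+105+3420 = 3545 | 3.732 | 3.73 |
| Amendment 2, Week 8 | 2+7+47 = 56 | 20+105+940 = 1065 | 1.121 | 1.11 |

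Three reproduce to two decimals. The fourth gives 1.12 whether rounded or truncated.

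**Could another input explain 1.11?** With 46 days at the top dose the result is 1045/950 = 1.10; with 48 days it is 1085/950 = 1.14. No whole number of days gives 1.11. A divisor between about 955 and 964 would, but the SAP prints 950, and 950 reproduces the other three.

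**Size of the slip.** 1.1211/1.11 = 1.010. On the SAP's own scale, a patient who took exactly the scheduled dose would show 101.0%.

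**Day counts.** SAP section 9.4 takes durations as the later date minus the earlier one, because intake starts in the afternoon and ends in the morning.

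- Day 1 p.m. to Day 181 a.m. is 181 − 1 = 180 days, which is what the extension sums use.
- On the same rule, 8 weeks is 56 days and ends on Day 57, which is what the Week 8 sums use.
- On the same rule, 26 weeks is 26 × 7 = 182 days and would end on Day 183.
- The extension implied by the SAP is 180 − 56 = 124 days; 18 weeks is 126.

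**Effect if 182 days is intended.** Two more days at the top dose add 2 × 10 × 2 = 40 mg/kg.

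- Amendment 2: 3585/3545 = 1.0113.
- Amendment 1: 3535/3495 = 1.0114.

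The divisor cancels in these ratios, so the effect of about 1.1% is the same on any divisor.

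**The case against.** The strongest reply is that this is immaterial, and much of that stands.

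- The analysis is descriptive. SAP section 8.5 plans no inference. Section 5 defines both analysis sets by having started the drug, with no compliance threshold.
- Visit windows move exposure more: ±4 days at Week 8 is 4/56 = 7.1%, and ±5 days at Week 26 is 5/182 = 2.7%. The difference is that windows scatter both ways, while a wrong constant does not.
- The divisor is a far larger matter. The protocol gives the product as 100 mg/mL. On that figure the Amendment 2 Week 8 plan is 1065/100 = 10.65 mL/kg, and 10.65/1.11 is about 959%.
- SAP 8.4 also plans a total based on visits actually performed, which uses neither the constants nor the fixed day counts. The compliance formula, however, points to PLANNED_DOSE.

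A reader might also infer three stronger things that the documents do not support.

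1. *Several constants are arithmetically wrong.* Only 1.11 fails on its own inputs.
2. *Compliance is inflated by 1% for everyone, whatever the divisor.* Amendment 1 patients who stop at Week 8 have a correct constant and a full 56 days. The 1.11 slip also disappears if the constant is recomputed from 1065 mg/kg on another divisor. It survives only if the printed figure is rescaled: 1.11 × 9.5 = 10.545, against 10.65.
3. *The 180 days is a counting error and should be 182.* It agrees with the Day 181 in SAP 4.3, which for Amendment 1 is the only end day visible, since that protocol version is not among the documents. It is a conflict between statements, and the documents do not settle which is meant.

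**Conclusion.** The point holds in a limited form. The Amendment 2 Week 8 constant is wrong on its printed inputs: 1.12, not 1.11 mL/kg. For those patients the planned dose is 1.0% too low and compliance is overstated by a factor of 1.010. This rests only on the arithmetic in SAP 8.4 and on taking its divisor as printed.

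The 180-day count is an unreconciled inconsistency between SAP 4.3 and 8.4 on one side and, on the other, the protocol's 26 weeks and the SAP's own 56-day Week 8 count. Its effect, about 1.1% for extension patients under either amendment, is conditional on 182 days being intended. If 180 days is intended, 3.68 and 3.73 stand on the SAP's divisor.

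Severity is low. The correction is worth making because it is nearly free and the figure goes into a reported table.

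**What to change.** 1. In SAP 8.4, change both occurrences of 1.11 to 1.12 on the printed inputs. If the divisor is revised, recompute from 1065 mg/kg; do not rescale the printed figure.
2. Program PLANNED_DOSE directly from the days and mg/kg of each schedule, so that no rounded constant enters the compliance calculation.
3. Reconcile the 180 days and Day 181 in SAP 4.3 and 8.4 with the 26 weeks and 18-week extension in the protocol. State the convention once and use it for both the Week 8 and the Week 26 sums.

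The cost is a short SAP correction and a small program change. No new data are needed and no other analysis changes.

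### SAP 8.4 gives an unweighed broken bottle the empty-bottle weight, so any drug spilled from it is counted as dose taken (0 to 31.6 mL per bottle, never downward)

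*SAP*

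**What the plan says.** In SAP 8.4 (Study drug exposure), total dose taken is a sum over bottles of 78 g minus the bottle weight, divided by 0.95 g/mL. Two anchor weights are fixed in the same table entry:

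- A full bottle weighs 78 g and contributes nothing: "Unused bottle', imputed weight to 78g".
- An empty bottle weighs 48 g and contributes its whole content: "Empty', imputed weight to 48g" (stated for unreturned bottles).

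For a returned bottle without a weight because of breakage, the rule is "Bottle broken', imputed weight to 48g". For unreturned bottles that are neither unused nor empty, the SAP fixes no weight: "Used per instructions', 'Not used per instructions', 'Unknown' must be reviewed during DRM".

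The result feeds global compliance, defined as "DOSE_TAKEN] / [PLANNED_DOSE". No review step, estimate of loss or sensitivity analysis is given for broken bottles.

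**The concern.** A broken bottle is one whose consumed volume is not known from its weight. Setting it to the empty weight resolves that uncertainty at the value most favourable to adherence. Whatever was lost in the breakage is added to the dose that the patient is said to have taken. The error is one-sided: it is zero if the bottle was already empty and positive otherwise.

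The rule also sits oddly beside its neighbour. An unreturned bottle of unknown status goes to the data review meeting, and so does one reported as used per instructions. A broken bottle, about whose consumption no more need be known, is settled automatically.

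At stake are total dose taken and global compliance. These are the only planned measures of the quantity of drug taken, and in an open-label pilot of about 25 patients a few affected bottles can shift a descriptive summary.

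**Working it through.** **Inputs**
- Full weight 78 g, empty weight 48 g, broken-bottle weight 48 g, density 0.95 g/mL (SAP 8.4).
- Planned dose, amendment 2: "Weight (in kg) * 1.11 mL/kg for patients who stopped the study at 8 weeks" and "Weight (in kg) * 3.73 mL/kg for patients who agreed to do the extension" (SAP 8.4).
- Cannabidiol concentration 100 mg/mL (Protocol 6.4 and 8.1); 30 mL bottles (Protocol 8.4.1).
- Body weight 80 kg, with a range of 60 to 100 kg. This is an assumption; the documents give no expected weight.

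**Step 1. Reproduce the SAP's planned-dose factors (amendment 2)**
- 8 weeks: 2×5×2 + 7×7.5×2 + 47×10×2 = 20 + 105 + 940 = 1065 mg/kg. 1065/950 = 1.121 mL/kg (printed as 1.11).
- 26 weeks: 20 + 105 + 171×10×2 = 3545 mg/kg. 3545/950 = 3.732 mL/kg (printed as 3.73).

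The factors reproduce, apart from rounding in the first. The divisor of 950 mg/mL matches the density of the solution (0.95 g/mL), whereas the protocol's concentration is 100 mg/mL. That is a separate problem. Both denominators are shown below so that the two effects are not confused.

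**Step 2. Volume credited to one bottle**
- Broken, at 48 g: (78 − 48)/0.95 = 31.58 mL, slightly above the nominal 30 mL.
- Empty, at 48 g: the same 31.58 mL.
- Unused, at 78 g: 0 mL.

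**Step 3. Overstatement**

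If a fraction s of the full content was spilled and the rest taken, the overstatement is 31.58 × s mL:

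| s | Overstatement (mL) |
|---|---|
| 0 | 0 |
| 0.25 | 7.9 |
| 0.5 | 15.8 |
| 0.75 | 23.7 |
| 1 | 31.6 |

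**Step 4. Largest effect on compliance from one bottle (s = 1, amendment 2)**

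At 80 kg the planned volume at 100 mg/mL is 1065 × 80/100 = 852 mL (8 weeks) and 3545 × 80/100 = 2836 mL (26 weeks). With the SAP's divisor of 950 it is 89.7 mL and 298.5 mL. The effect is 31.58 divided by each:

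| Denominator | 8 weeks, 80 kg | 8 weeks, 60 to 100 kg | 26 weeks, 80 kg | 26 weeks, 60 to 100 kg |
|---|---|---|---|---|
| 100 mg/mL | 3.7 points | 4.9 to 3.0 | 1.1 points | 1.5 to 0.9 |
| 950 mg/mL (as printed) | 35.2 points | 47.0 to 28.2 | 10.6 points | 14.1 to 8.5 |

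**Step 5. Scale**

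At 10 mg/kg b.i.d. an 80 kg patient uses 20 × 80/100 = 16 mL per day, so 31.58 mL is 1.97 days of drug. The planned volume corresponds to 852/30 = 28.4 bottles over 8 weeks and 2836/30 = 94.5 over 26 weeks.

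**The case against.** The strongest reply is that very little depends on this rule, and much of that reply stands.

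- **Reach.** A reader might infer that exposure as a whole, or the efficacy and safety results, rest on the affected figures. The documents do not support that. SAP 8.4 also tabulates days on drug, premature stops and highest tolerated dose, none of which uses bottle weights. Both analysis sets in SAP section 5 require only enrolment and a start of treatment. No compliance threshold is defined there, and SAP 8.5 plans no inferential analysis.
- **Size.** A reader might also take 31.6 mL as the error for every broken bottle. It is the credit given; the error is only the part that was spilled, which may be none.
- **Frequency.** The documents give no count or expected rate of breakage. The rule needs a bottle that is returned, unweighed and recorded as broken, so the actual effect may be nil.
- **Replacement.** It is tempting to add that a replacement bottle would be counted twice. SAP 8.4 states no replacement rule, and counting drug taken from a replacement would be correct.
- **Status of the rule.** SAP 9.2 allows imputation where it is stated, and here it is stated. Breakage is also a documented reason, not an undetermined status, so the contrast with "Unknown' must be reviewed during DRM" is one of unequal treatment and not a contradiction.

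What remains is that knowing a bottle broke does not tell us how much had been taken from it. The SAP picks the upper end without a reason and without showing the lower end.

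**Conclusion.** The point holds as a small, one-sided bookkeeping error. Each returned, unweighed broken bottle overstates dose taken by 0 to 31.6 mL. For an assumed 80 kg patient under amendment 2, the maximum per bottle is 3.7% of the 8-week or 1.1% of the 26-week planned volume at 100 mg/mL. The figures of about 35 and 11 percentage points on the printed 950 mg/mL denominator are what the SAP formula would yield, but their size comes from that denominator and should not be charged to the broken-bottle rule.

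The only listed output affected is the descriptive exposure table (Table 15). The result rests on the assumed body weights and on the unknown spilled fraction. The total effect across the trial cannot be stated, because the number of broken bottles is not given.

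**What to change.** In SAP 8.4:

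1. Remove the automatic 48 g for broken bottles and send them to the data review meeting, as is already done for unreturned bottles of unknown status. Use a documented volume where one exists.
2. Where nothing is documented, report dose taken and global compliance under both bounds, 48 g (all taken) and 78 g (none taken).
3. Footnote the number of broken bottles in Table 15.

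Two shortcuts should be avoided. Assigning the volume from the prescribed dose assumes the adherence that is being measured. Dispensing dates do not help either: bottles are supplied per assessment period, and from Week 3 to Week 8 an 80 kg patient needs about 35 × 16/30 = 18.7 of them. Leaving the bottle out of the sum silently credits 0 mL and reverses the bias.

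The rule should be settled before the first data review meeting, because SAP section 6 locks the data up to Week 8 after it. The cost is one line in the SAP, a short agenda item at meetings already planned, and compliance shown as a range for the affected patients. No new data are needed.

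### SAP 8.4 scores an unweighed broken bottle as empty, so any drug left in it when it broke counts as taken in the exposure table

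*SAP*

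**What the plan says.** The exposure table in SAP 8.4 computes total dose taken by summing (78 g − bottle weight)/0.95 g/mL over bottles.

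- **Returned bottles.** The clause opens "If there is no bottle weight and the reason is" and then gives two cases: "Bottle broken', imputed weight to 48g" and "Unused bottle', imputed weight to 78g".
- **Unreturned bottles.** An empty one is handled by "Empty', imputed weight to 48g", and an unused one is set to 78 g. Any other status (used as instructed, not used as instructed, unknown) "must be reviewed during DRM".
- **Compliance.** Global compliance is "DOSE_TAKEN] / [PLANNED_DOSE".
- **Planned dose.** Under Amendment 2 the planned dose is "Weight (in kg) * 3.73 mL/kg for patients who agreed to do the extension" or "Weight (in kg) * 1.11 mL/kg for patients who stopped the study at 8 weeks".

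Protocol 11.4 plans no imputation of missing data. SAP 9.2 allows imputation where the SAP states it, and SAP 8.4 does state this one, but without giving a reason for the value or a sensitivity analysis.

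**The concern.** On the SAP's weight scale, 78 g means nothing used and 48 g means everything used. A broken bottle with no recorded weight shows neither. Whatever was in it when it broke was lost, not swallowed, yet the rule assigns the largest intake the scale allows. Any error is therefore upward.

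The neighbouring rule is more cautious: unreturned bottles of uncertain status go to case review. Among bottles of uncertain content for which SAP 8.4 gives a rule, the broken ones are the only group automatically scored as fully consumed.

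At stake are two descriptive lines in Table 15, total dose taken and global compliance. With about 25 patients and no inferential analysis, readers will take these figures at face value when judging how much drug the safety experience rests on.

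**Working it through.** **Inputs.** Full bottle 78 g, empty or broken bottle 48 g, density 0.95 g/mL (SAP 8.4). Dosing days by level under Amendment 2 (SAP 8.4). Concentration 100 mg/mL (Protocol 6.4 and 8.1). Nominal fill 30 mL (Protocol 8.4.1). Body weights of 60, 80 and 100 kg are my assumption; the documents give none.

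**1. Reproduce the SAP's planned dose (Amendment 2).**
- 26 weeks: 2×5×2 + 7×7.5×2 + 171×10×2 = 20 + 105 + 3420 = 3545 mg/kg. Then 3545/950 = 3.73 mL/kg, as stated.
- 8 weeks: 20 + 105 + 47×10×2 = 1065 mg/kg. Then 1065/950 = 1.12 mL/kg, against 1.11 stated, a difference of 1%.

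**2. Volume credited to a broken bottle.** (78 − 48)/0.95 = 31.58 mL, the same as for an empty bottle. An unused bottle gives (78 − 78)/0.95 = 0 mL. The credit is 1.58 mL above the nominal 30 mL, because 30 mL × 0.95 = 28.5 g rather than 30 g. That small gap affects every empty bottle alike.

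**3. Overstatement.** If a fraction f of the content had been taken before the break, the excess on the SAP's own scale is 31.58 × (1 − f) mL:

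| f | Excess credited (mL) |
|---|---|
| 0 | 31.58 |
| 0.25 | 23.68 |
| 0.50 | 15.79 |
| 0.75 | 7.89 |
| 1 | 0 |

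**4. Largest effect relative to planned volume.** At 100 mg/mL the planned volumes are 3545/100 = 35.45 mL/kg and 1065/100 = 10.65 mL/kg.

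| Weight | 26-week volume | One bottle | 8-week volume | One bottle |
|---|---|---|---|---|
| 60 kg | 2127 mL | 1.5% | 639 mL | 4.9% |
| 80 kg | 2836 mL | 1.1% | 852 mL | 3.7% |
| 100 kg | 3545 mL | 0.9% | 1065 mL | 3.0% |

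The Amendment 1 schedule gives slightly larger 8-week figures: 1015 mg/kg, so 10.15 mL/kg, and 31.58/609 = 5.2% at 60 kg.

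**5. On the SAP's printed constants.** At 80 kg, 31.58/(80 × 3.73) = 31.58/298.4 = 10.6 compliance points over 26 weeks. On that scale, however, full intake at 100 mg/mL would read 35.45/3.73 = 9.50, or 950%. The relative effect is still 10.6/950 = 1.1%. The large number comes from the 950 mg/mL divisor, not from the broken-bottle rule.

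**The case against.** The strongest reply is that this is a small, stated convention with little reach, and much of that stands.

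- **The bottle may have been empty.** The SAP does not say when a bottle broke or what it held. If it broke after use or on the way back to the site, 48 g is right and the error is zero. The rule also applies only where no weight was recorded, and the number of such bottles is unknown and could be nil.
- **The comparison is between two rules.** The referral to data review is written for unreturned bottles and the 48 g rule for returned ones. This is uneven treatment, not a contradiction.
- **The usual effect is about 1%.** Entry to the extension is the default (Protocol 6.2), so the 26-week denominator applies to most patients. One fully lost bottle at 80 kg, averaged over 25 patients, moves mean compliance by 1.1/25, or about 0.04 points.

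A reader might infer two stronger things, and the documents support neither.

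- **That the efficacy and safety results rest on inflated exposure.** Membership of the full analysis and safety sets depends only on starting drug (SAP 5.1 and 5.2), and SAP 5 defines no per-protocol set or compliance threshold. Days on drug come from dates, and highest tolerated dose from dose level. The analyses in SAP 8.5 and 8.6 do not use bottle weights.
- **That a replacement bottle makes one dosing period count twice.** No replacement procedure for broken bottles is described. Protocol 8.4.1 says only that new bottles are supplied for each assessment period. In any case the excess from a broken bottle cannot exceed what it still held.

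The direction of the error survives these points. The rule puts an unknown at its most favourable extreme, and I found nothing else in the SAP that offsets it.

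**Conclusion.** The point holds as a minor, one-directional flaw in a descriptive derivation. Each unweighed broken bottle adds an excess of between 0 and 31.6 mL to dose taken and to the numerator of compliance. Under Amendment 2 that is at most 0.9 to 1.5% of planned volume over 26 weeks, or 3.0 to 4.9% over 8 weeks for patients who stop there.

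These percentages rest on assumed weights of 60 to 100 kg and on planned volume at the protocol's 100 mg/mL. The SAP's 950 mg/mL divisor is a separate and much larger discrepancy in the same compliance ratio, and must be reconciled on its own account. The total effect cannot be stated without the number of broken bottles. No efficacy or safety endpoint changes.

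**What to change.** In SAP 8.4, delete the automatic 48 g for broken bottles and add them to the statuses referred to the data review meeting. Decide the amount used from the dispensing log (Protocol 8.3 and 14.5) and the accountability records kept at each visit after the start of treatment (Protocol 9.2.12). Bottles returned by Week 8 belong in the first of the two meetings in SAP 6, since data up to that visit are locked afterwards.

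Where the amount cannot be determined, report that patient's dose taken and compliance at both bounds, 0 mL and a full bottle, and state in Table 15 how many bottles are involved. Two shortcuts should be avoided:

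- Leaving the bottle out of the sum is arithmetically the same as 78 g, or nothing taken, which is the opposite extreme.
- Filling in the prescribed dose up to the break assumes the compliance that is being measured.

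The cost is a line of SAP text and a few more bottles in a review already planned. Compliance may look slightly lower.
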